### 11.1.1. Sample Size Justification - Arm A (TSA/HA)

Benchmark and Objectives for Clinical Investigation						
Endpoint	Non-inferiority (equal or better) of the ASES Shoulder Score in relation to the officially cleared indications in comparison to respective clinical outcome data in the scientific literature.					
	Meta-analysis by Shukla et. al., 2016 [1]					
Estimated drop-out rate	56% (confirmed by Medical Expert, see Cuff et al. [2])					
Benchmark Sources & Values ASES [points] for Arm A (TSA/HA)						
Values from Shukla et. al used that were given for Hemiarthroplasty						
Source		Mean	Std. Dev.			
No.	Title					
1	Sebastia-Forcada, 2014 [3]	N/A	N/A			
2	Baudi, 2014 [4]	51.3	25.4			
3	Chalmers, 2014 [5]	66.0	31.0			
4	Cuff, 2013 [6]	62.0	14.0			
5	Garrigues, 2012 [7]	47.4	12.75			
6	Young, 2010 [8]	67.0	18.5			
7	Gallinet, 2009 [9]	N/A	N/A			
Identified Cleared Indications (Arm A & B)						
No.	Indication					
1	Aseptic necrosis of the humeral head					
2	Painful, disabling joint disease of the shoulder resulting from degenerative arthritis, rheumatoid arthritis or post-traumatic arthritis					
3	Proximal humeral fractures and/or dislocation					
4	Clinical management problems where arthrodesis or alternative reconstructive techniques are less likely to achieve satisfactory results					
5	Revision of previous unsuccessful total shoulder replacement, resurfacing or other procedure					
Explorative Analysis - ASES (single group) - for Arm A (TSA/HA)						
Acceptance Criteria						
Confidence Interval (CI)		0.95 (95%) two-sided				
Software Used		IBM SPSS V20				

Descriptives						
Post-Op ASES Mean		Statistic	Std. Error			
Mean		58,7400	3,97185			
95% Confidence Interval for Mean	Lower Bound	47,7124				
	Upper Bound	69,7676				
Median		62,0000				
Std. Deviation		8,88133				
Minimum		47,40				
Maximum		67,00				
Interquartile Range		17,15				
Post-Op ASES Std.Dev.	Mean	20,3300	3,46719			
		Red line: Pooled mean ASES Blue lines: 95% CI of pooled mean ASES Black line: Pooled median pooled ASES Box: Interquartile Range Green Line: Pooled mean ASES minus std. dev. ASES $58.74 - 20.33 = 38.41$ points				
Acceptance Criteria for Sample Size Calculation						
Significance Level ( $\alpha$ )	0.05 (5%)					
Power (1- $\beta$ )	0.80 (80%)					
Confidence Interval (CI)	0.95 (95%)					
Tails	2					

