Path	Non-inferiority – ReUnion RFX Arm A (TSA/HA) (A) $\geq$ Benchmark (B, explorative analysis in this document)					
Hypotheses Pair	Null ( $H_0$ )		A – B $< -\theta$			
	Alternative ( $H_1$ )		A – B $\geq -\theta$			
Benchmark Timepoint	24 months postoperative					
Benchmark no. of sources	5					
Benchmark Mean	58.74 (pooled mean ASES [points])					
Benchmark Std. Dev.	20.33 (pooled std. dev. ASES [points])					
Benchmark Value	Pooled mean ASES minus pooled std. dev. ASES					
Non-Inferiority Margin (- $\theta$ )	$58.74 - 20.33 = 38.41$ points					
Software Used	IBM SPSS Sample Power V3.0					
IBM SPSS Sample Power Output						
One goal of the proposed clinical investigation is to test the null hypothesis that the population mean is 58.74 points. The criterion for significance (alpha) has been set at 0.05. The test is 2-tailed, which means that effects in both directions will be interpreted. With the proposed sample size of 10 cases, the clinical investigation will have power of 80.3% to yield a statistically significant result. This computation assumes that the population from which the sample will be drawn has a mean of 58.74 points with a standard deviation of 20.33 points. The observed value will be tested against a theoretical value (constant, non-inferiority margin) of 38.41 points.						

[figure not shown]
Estimated overall drop-out rate is 56% which leads to the requirement of enrolling an additional 6 subjects into the clinical investigation.

Sample Size	Overall number of subjects to be enrolled: 16 subjects (rounded up to 20 subjects)
Overall Sample Size (multiplied by number of indications = 5)	100 subjects

Table 2a: Sample Size Justification Arm A (TSA/HA)

[figure not shown]

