### 11.3.2. Primary Analysis / Endpoint

The objective of the clinical investigation is to demonstrate the non-inferiority (equal or better) of the ASES Shoulder Score in relationship to the officially cleared indications in comparison to respective clinical outcome data in the scientific literature.

Data collection of ASES Shoulder Score will be collected according to the schedule in Table 1, Schedule of Events. This will be repeated annually in all subjects who have the prosthesis with full or partial implant survival (including all subjects without removal of all endo-prosthesis components).

The 24 months postoperative results for subjects implanted with ReUnion RFX System will be compared to a historical group and results reported by respective clinical outcome data in the scientific literature.

[figure not shown]
Higher ASES Shoulder Score results are linked to better subject results and vice versa.

The clinical investigation endpoint is non-inferiority to the control, meaning the clinical investigation result should be equal or better than the control. In this clinical investigation, an equal or better ASES Shoulder Score result means equal or more ( $\geq$ ). As only results from samples will be captured, results are mostly estimates of the true population parameter. These

estimates vary by a certain area, where it is expected that the true population parameter falls within. Based on this, it is required to specify a lower limit for the acceptable difference or zone of indifference, denoted as  $-\theta$ .

Hypotheses are developed to allow for a comparison of the 24 months postoperative ASES Shoulder Score effectiveness/performance between the two underlying populations. The 24 months post-operative ASES Shoulder Score is the primary endpoint of this clinical investigation. Hypothesis tests will be one-sided with a significance level  $\alpha$  of 5%.

[figure not shown]
Table 3a: Arm A (TSA/HA)

Hypothesis	Equations	Interpretation
Null ( $H_0$ )	$A - B < -\theta$	Central tendency of A is inferior to the central tendency of B.
	ReUnion RFX System (TSA/HA) – Control (Benchmark) $< -\theta$	
Alternative ( $H_1$ )	$A - B \geq -\theta$	Central tendency of A is non-inferior to the central tendency of B.
	ReUnion RFX System (TSA/HA) – Control (Benchmark) $\geq -\theta$	
		
Possible Evidence (p)	Possible Decisions	Possible Conclusions – ASES score

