p-value $> \alpha$ (0.05)	Fail to reject null hypothesis ( $H_0$ )	ReUnion RFX System (TSA/HA) $<$ Control (Benchmark) Insufficient evidence to reject the null hypothesis ( $H_0: A - B < -\theta$ ) at the pre-determined significance level of 5%.
p-value $\leq \alpha$ (0.05)	Reject null hypothesis ( $H_1$ )	ReUnion RFX System (TSA/HA) $\geq$ Control (Benchmark) Sufficient evidence to reject the null hypothesis ( $H_0: A - B < -\theta$ ) at the pre-determined significance level of 5%.

The primary objective of the clinical investigation is to demonstrate non-inferiority of the ASES Shoulder Score at 24 months post-operative compared to the benchmark literature for Arm A. The 24 months mean ASES Shoulder Score result of the RFX System (TSA/HA) will be compared to the pooled postoperative mean estimate of the control group (58.74 points). The pooled standard deviation of the post-operative ASES Shoulder Score result of the benchmark (20.33 points) was used to determine lower limit. The lower maximum acceptable difference ( $-\theta$ ) is 38.41 points (mean of control -  $\theta$  or  $58.74 - 20.33 = 38.41$  points).

Based on the underlying distribution of the data and the result of the normality assessment, either the parametric one-sample t-test or the non-parametric one-sample sign test will be used to compare the 24 months postoperative ASES Shoulder Score results of the ReUnion RFX System (RSA) against the value of 38.41 points.

Table 4a: Arm B (RSA)

Hypothesis	Equations	Interpretation
Null ( $H_0$ )	$A - B < -\theta$	Central tendency of A is inferior to the central tendency of B.
	ReUnion RFX System (RSA) – Control (Benchmark) $< -\theta$	
Alternative ( $H_1$ )	$A - B \geq -\theta$	Central tendency of A is non-inferior to the central tendency of B.
	ReUnion RFX System (RSA) – Control (Benchmark) $\geq -\theta$	
		
Possible Evidence (p)	Possible Decisions	Possible Conclusions – ASES score
p-value $> \alpha$ (0.05)	Fail to reject null hypothesis ( $H_0$ )	ReUnion RFX System (RSA) $<$ Control (Benchmark) Insufficient evidence to reject the null hypothesis ( $H_0: A - B < -\theta$ ) at the pre-determined significance level of 5%.
p-value $\leq \alpha$ (0.05)	Reject null hypothesis ( $H_1$ )	ReUnion RFX System (RSA) $\geq$ Control (Benchmark) Sufficient evidence to reject the null hypothesis ( $H_0: A - B < -\theta$ ) at the pre-determined significance level of 5%.

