3.1.1. Primary Analysis / Endpoint

The objective of the clinical investigation is to demonstrate the non-inferiority (equal or better) of the ASES Shoulder Score in relationship to the officially cleared indications in comparison to respective clinical outcome data in the scientific literature.

Data collection of ASES Shoulder Score will be collected according to the schedule in Table 1, Schedule of Events. This will be repeated annually in all subjects who have the prosthesis with

full or partial implant survival (including all subjects without removal of all endo-prosthesis components).

The 24 months postoperative results for subjects implanted with ReUnion RFX System will be compared to a historical group and results reported by respective clinical outcome data in the scientific literature.

Higher ASES Shoulder Score results are linked to better subject results and vice versa.

The clinical investigation endpoint is non-inferiority to the control, meaning the clinical investigation result should be equal or better than the control. In this clinical investigation, an equal or better ASES Shoulder Score result means equal or more (\geq). As only results from samples will be captured, results are mostly estimates of the true population parameter. These estimates vary by a certain area, where it is expected that the true population parameter falls within. Based on this, it is required to specify a lower limit for the acceptable difference or zone of indifference, denoted as $-\theta$.

Hypotheses are developed to allow for a comparison of the 24 months postoperative ASES Shoulder Score effectiveness/performance between the two underlying populations. The 24 months post-operative ASES Shoulder Score is the primary endpoint of this clinical investigation. Hypothesis tests will be one-sided with a significance level α of 5%.

Arm A (TSA/HA)		
Hypothesis	Equations	Interpretation
Null (H_0)	$A - B < -\theta$	Central tendency of A is inferior to the central tendency of B.
	ReUnion RFX System (TSA/HA) – Control (Benchmark) $< -\theta$	
Alternative (H_1)	$A - B \geq -\theta$	Central tendency of A is non-inferior to the central tendency of B.
	ReUnion RFX System (TSA/HA) – Control (Benchmark) $\geq -\theta$	
Possible Evidence (p)	Possible Decisions	Possible Conclusions – ASES score

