$p\text{-value} > \alpha (0.05)$	Fail to reject null hypothesis (H_0)	ReUnion RFX System (TSA/HA) $<$ Control (Benchmark) Insufficient evidence to reject the null hypothesis ($H_0: A - B < -\theta$) at the pre-determined significance level of 5%.
$p\text{-value} \leq \alpha (0.05)$	Reject null hypothesis (H_1)	ReUnion RFX System (TSA/HA) \geq Control (Benchmark)

		Sufficient evidence to reject the null hypothesis ($H_0: A - B < -\theta$) at the pre-determined significance level of 5%.
--	--	--

Table 3.1.1.1: Arm A (TSA/HA)

The primary objective of the clinical investigation is to demonstrate non-inferiority of the ASES Shoulder Score at 24 months post-operative compared to the benchmark literature for Arm A. The 24 months mean ASES Shoulder Score result of the RFX System (TSA/HA) will be compared to the pooled postoperative mean estimate of the control group (58.74 points). The pooled standard deviation of the post-operative ASES Shoulder Score result of the benchmark (20.33 points) was used to determine lower limit. The lower maximum acceptable difference ($-\theta$) is 38.41 points (mean of control $-\theta$ or $58.74 - 20.33 = 38.41$ points).

Based on the underlying distribution of the data and the result of the normality assessment, either the parametric one-sample t-test or the non-parametric one-sample sign test will be used to compare the 24 months postoperative ASES Shoulder Score results of the ReUnion RFX System (TSA/HA) against the value of 38.41 points.

Arm B (RSA)		
Hypothesis	Equations	Interpretation
Null (H_0)	$A - B < -\theta$	Central tendency of A is inferior to the central tendency of B.
	ReUnion RFX System (RSA) – Control (Benchmark) $< -\theta$	
Alternative (H_1)	$A - B \geq -\theta$	Central tendency of A is non-inferior to the central tendency of B.
	ReUnion RFX System (RSA) – Control (Benchmark) $\geq -\theta$	
Possible Evidence (p)	Possible Decisions	Possible Conclusions – ASES score
p-value $> \alpha$ (0.05)	Fail to reject null hypothesis (H_0)	ReUnion RFX System (RSA) $<$ Control (Benchmark) Insufficient evidence to reject the null hypothesis ($H_0: A - B < -\theta$) at the pre-determined significance level of 5%.
p-value $\leq \alpha$ (0.05)	Reject null hypothesis (H_1)	ReUnion RFX System (RSA) \geq Control (Benchmark) Sufficient evidence to reject the null hypothesis ($H_0: A - B < -\theta$) at the pre-determined significance level of 5%.

Table 3.1.1.2: Arm B (RSA)

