Confidence Interval (CI)	0.95 (95%)	
Tails	2	
Path	Non-inferiority – ReUnion RFX Arm A (TSA/HA) (A) ≥ Benchmark (B, explorative analysis in this document)	
Hypotheses Pair	Null (H ₀)	A – B < -θ
	Alternative (H ₁)	A – B ≥ -θ
Benchmark Timepoint	24 months postoperative	
Benchmark no. of sources	5	
Benchmark Mean	58.74 (pooled mean ASES [points])	
Benchmark Std. Dev.	20.33 (pooled std. dev. ASES [points])	
Benchmark Value Non-Inferiority Margin (-θ)	Pooled mean ASES minus pooled std. dev. ASES 58.74 – 20.33 = 38.41 points	
Software Used	IBM SPSS Sample Power V3.0	
IBM SPSS Sample Power Output		

One goal of the proposed clinical investigation is to test the null hypothesis that the population mean is 58.74 points. The criterion for significance (alpha) has been set at 0.05. The test is 2-tailed, which means that effects in both directions will be interpreted. With the proposed sample size of 10 cases, the clinical investigation will have power of 80.3% to yield a statistically significant result. This computation assumes that the population from which the sample will be drawn has a mean of 58.74 points with a standard deviation of 20.33 points. The observed value will be tested against a theoretical value (constant, non-inferiority margin) of 38.41 points.
		
IBM SPSS Sample Power Output – Screenshot		

Estimated overall drop-out rate is 56% which leads to the requirement of enrolling an additional 6 subjects into the clinical investigation.
		
Sample Size	Overall number of subjects to be enrolled: 16 subjects (rounded up to 20 subjects)	
Overall Sample Size (multiplied by number of indications = 5)	100 subjects	

Table 3.2.1: Sample Size Justification Arm A (TSA/HA)

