3.2.2. Sample Size Justification - Arm B (RSA)

Benchmark and Objectives for Clinical Investigation	
Endpoint	
Non-inferiority (equal or better) of the ASES Shoulder Score in relation to the officially cleared indications in comparison to respective clinical outcome data in the scientific literature.
 
Meta-analysis by Shukla et al., 2016 [1]

Estimated drop-out rate	56% (confirmed by Medical Expert, see Cuff et al. [2])

Benchmark Sources & Values ASES [points] for Arm B (RSA)				
Source		Mean	Std. Dev.	Comments
No.	Title			
1	Sebastia-Forcada, 2014 [3]	N/A	N/A	No ASES score
2	Baudi, 2014 [4]	69.3	25.4	
3	Chalmers, 2014 [5]	80.0	11.0	
4	Cuff, 2013 [6]	77.0	3.75	
5	Garrigues, 2012 [7]	81.1	3.25	
6	Young, 2010 [8]	65.0	12.0	
7	Gallinet,2009 [9]	N/A	N/A	No ASES score
Identified Cleared Indications (Arm A & B)				
No.	Indication			
1	Aseptic necrosis of the humeral head			
2	Painful, disabling joint disease of the shoulder resulting from: degenerative arthritis, rheumatoid arthritis, or post-traumatic arthritis			
3	Proximal humeral fractures and/or dislocation			
4	Clinical management problems where arthrodesis or alternative reconstructive techniques are less likely to achieve satisfactory results			
5	Revision of previous unsuccessful total shoulder replacement, resurfacing or other procedure			
Explorative Analysis - ASES (single group) - for Arm B (RSA)				
Acceptance Criteria				
Confidence Interval (CI)			0.95 (95%) two-sided	
Software Used			IBM SPSS V20	
Descriptives				
			Statistic	Std. Error
Post-Op ASES Mean	Mean		74,4800	3,14124
	95% Confidence Interval for Mean	Lower Bound	65,7585	
		Upper Bound	83,2015	
	Median		77,0000	
	Std. Deviation		7,02403	
	Minimum		65,00	
	Maximum		81,10	
	Interquartile Range		13,40	
Post-Op ASES Std.Dev.	Mean		11,0800	4,00595
			
Red line: Pooled mean ASES
 
Blue lines: 95% CI of pooled mean ASES
 
Black line: Pooled median pooled ASES
 
Box: Interquartile Range
 
Green Line: Pooled mean ASES minus pooled std. dev. ASES
 
$74.48 - 11.08 = 63.40$ points
	
Acceptance Criteria for Sample Size Calculation				
Significance Level (α)		0.05 (5%)		
Power (1- β)		0.80 (80%)		
Confidence Interval (CI)		0.95 (95%)		

Tails	2	
Path	Non-inferiority – ReUnion RFX Arm B (RSA) (A) ≥ Benchmark (B, explorative analysis in this document)	
Hypotheses Pair	Null (H ₀)	A – B < -θ
	Alternative (H ₁)	A – B ≥ -θ
Benchmark Timepoint	24 months postoperative	
Benchmark no. of sources	5	

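### The pre-written primary conclusions (RFX ≥ Control if p ≤ 0.05, RFX < Control if p > 0.05) do not follow from tests against the benchmark minus one SD

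*Protocol*

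**What the plan says.** Protocol 11.3.2 explains the endpoint as non-inferiority, "meaning the clinical investigation result should be equal or better than the control". SAP 3.1.1 repeats this and adds that "an equal or better ASES Shoulder Score result means equal or more", with the ≥ sign. Both sections then set H0: A − B < −θ against H1: A − B ≥ −θ and describe H1 as non-inferior.

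The decision tables in the same sections print a conclusion for each outcome and arm:

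- p ≤ 0.05: RFX ≥, followed by "Control (Benchmark) Sufficient evidence to reject the null hypothesis" (Protocol; same in the SAP).
- p > 0.05: RFX <, followed by "Control (Benchmark) Insufficient evidence to reject the null hypothesis" (SAP; same in the Protocol).

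The four sample-size tables (Protocol 11.1.1 and 11.1.2, SAP 3.2.1 and 3.2.2) use the same definition in the endpoint row: "Non-inferiority (equal or better) of the ASES Shoulder Score in relation to the officially cleared indications". Their Path rows read "ReUnion RFX Arm A (TSA/HA) (A) ≥ Benchmark (B, explorative analysis in this document" for Arm A and "ReUnion RFX Arm B (RSA) (A) ≥ Benchmark (B, explorative analysis in this document" for Arm B.

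The tests themselves (Protocol 8.1, 8.2 and 11.3.2; SAP 3.1.1 and 6.6) are a one-sample t-test or sign test against 38.41 points in Arm A and 63.40 points in Arm B.

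**The concern.** The printed conclusions are not the ones the hypotheses allow. Rejecting A − B < −θ says that RFX is not worse than the benchmark by more than θ. It does not say that RFX is at least as good as the benchmark. Failing to reject says nothing about RFX being worse; it is an inconclusive result.

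Both errors sit in the decision rule for the primary endpoint of a study that Protocol section 13 says is run to support safety and performance under the EU MDR. Followed literally, the plan can report a device whose mean is clearly below the benchmark as equal or better, and an inconclusive arm as worse than control.

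**Working it through.** **Inputs (Protocol 11.1.1 and 11.1.2; SAP 3.2.1 and 3.2.2).** Arm A: benchmark mean 58.74, SD 20.33, test value 38.41, SE of the benchmark mean 3.97185. Arm B: 74.48, 11.08, 63.40 and 3.14124. Each benchmark rests on 5 sources. Protocol 11.3.2 sets a one-sided α of 0.05.

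**The plan's own figures reproduce.** 58.74 − 20.33 = 38.41 and 74.48 − 11.08 = 63.40. The effect is 20.33/20.33 = 11.08/11.08 = 1 SD. With n = 10 and 9 df, the noncentral t gives 80.31% power two-sided (stated: 80.3%) and 89.75% one-sided. This is power against the benchmark minus one SD. A one-sided test of RFX against 58.74 or 74.48 itself would reject in only 5% of trials if RFX equalled the benchmark.

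**Choice of n.** The documents do not split the 100 subjects by arm. I use n = 10 (the plan's evaluable number), n = 50 (half of 100) and n = 22 (50 × 0.44, after 56% drop-out). The observed SD is set equal to the benchmark SD.

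**Lowest mean that prints RFX ≥ Control** = test value + t(0.95, n−1) × SD/√n. For Arm A at n = 10: 38.41 + 1.833 × 6.429 = 50.19.

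| Arm | n | Lowest passing mean | Difference from benchmark | 95% CI, benchmark fixed | 95% CI, benchmark SE added |
|---|---|---|---|---|---|
| A | 10 | 50.19 | −8.55 | −23.09 to 6.00 | −24.88 to 7.79 |
| A | 22 | 45.87 | −12.87 | −21.89 to −3.86 | −25.39 to −0.35 |
| A | 50 | 43.23 | −15.51 | −21.29 to −9.73 | −26.59 to −4.43 |
| B | 10 | 69.82 | −4.66 | −12.58 to 3.27 | −14.92 to 5.60 |
| B | 22 | 67.46 | −7.02 | −11.93 to −2.10 | −15.87 to 1.84 |
| B | 50 | 66.03 | −8.45 | −11.60 to −5.30 | −16.97 to 0.07 |

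The last column uses √(SD²/n + SE²) with Satterthwaite df (4 df for the benchmark). With the benchmark fixed, the Arm A interval excludes zero from n = 16 (−22.25 to −0.59). With the benchmark SE added, the Arm A upper limit is still +0.35 at n = 20 and is −0.35 at n = 22. In Arm B the interval with the benchmark SE includes zero at every n from 10 to 50.

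**Probability that a device half an SD worse (10.2 points in A, 5.5 in B) prints RFX ≥ Control:** 0.43 at n = 10, 0.73 at n = 22, 0.97 at n = 50.

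**Probability that a device equal to the benchmark prints RFX < Control:** 0.102 at n = 10, 0.015 at n = 16, 0.002 at n = 22. Under the two-tailed setting it is 0.197 at n = 10.

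**Two-tailed setting of the sample-size tables**, using t(0.975, n−1): the lowest passing means at n = 10 / 22 / 50 are 52.95 / 47.42 / 44.19 in Arm A and 71.33 / 68.31 / 66.55 in Arm B. All are still below the benchmark.

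**Sign-test branch** (exact, one-sided, no ties): 9 of 10 (p = 0.011), 16 of 22 (p = 0.026) or 32 of 50 (p = 0.032) scores above 38.41 / 63.40 print RFX ≥ Control, whether or not any score reaches 58.74 / 74.48.

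**The case against.** The best defence is that only a label is wrong. The hypotheses are stated correctly, H1 is described as non-inferior, and the sentence in the same cell refers correctly to H0: A − B < −θ. SAP 6.6 carries only the test, and Protocol 8.1 and 8.2 speak only of non-inferiority. The text also introduces an indifference zone, so equal might mean equal within that zone. In the sample-size tables the row labelled Benchmark Value holds 38.41 / 63.40, so the Path row could be read as describing the actual test.

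These points show that the test is sound, but they leave two incompatible conclusions side by side in the primary decision table. The ≥ sign is expressly defined as equal or more. The B in the Path row is the B of A − B < −θ, so it must be the benchmark mean. The 95% CI of the mean already planned for each visit would let a reader see a shortfall, but it would not correct the printed conclusion.

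Some objections to the size of the effect do stand. The two harms do not peak at the same n: at n = 10 the interval at the threshold includes zero, so ≥ Control is unsupported rather than contradicted; by n = 22, an equal device is almost never labelled worse. The table describes results exactly at the threshold, not expected results. And n = 22 assumes an even split and the full 56% loss by 24 months, although the source cited for that rate has at least 10 years of follow-up. Retention as implied by the plan's own inflation (10 of 16) would leave about 31 of 50. There the lowest passing Arm A mean is 44.61, with an interval of −25.84 to −2.42 (benchmark SE added), so the conclusion does not depend on n = 22.

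**Conclusion.** The concern holds and must be fixed in both documents. A significant result supports only that the central tendency of the 24-month ASES score is not below the benchmark by more than 20.33 (Arm A) or 11.08 (Arm B) points. A non-significant result supports only that non-inferiority was not shown.

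The mislabelling does not depend on n, sidedness or choice of test; its size does. In Arm A the label ≥ Control can attach to a mean 8.5 (n = 10) to 15.5 (n = 50) points below the benchmark. In Arm B the gap is 4.7 to 8.5 points, and the effect is mild once the benchmark's uncertainty is counted. These figures assume the t-test branch, a one-sided 0.05 level and an observed SD equal to the benchmark SD.

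Related slips should be cleared at the same time:

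- −θ is given as 38.41 / 63.40, although the plan's own subtraction makes θ 20.33 / 11.08.
- The sample-size text names 58.74 / 74.48 as the null values.
- The sample-size tables are two-tailed, while 11.3.2 and SAP 3.1.1 are one-sided.
- Protocol 11.3.2 names RSA in the sentence that tests against 38.41.
- The decision tables tag rejection of the null as H1.
- Sampling variation is the reason given for having a limit. The benchmark SEs of 3.97 / 3.14 do not explain a margin of one between-patient SD.

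**What to change.** **Must be changed**

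1. In Protocol 11.1.1, 11.1.2 and 11.3.2 and SAP 3.1.1, 3.2.1 and 3.2.2, stop defining non-inferiority as equality or better. Define it as: the central tendency of 24-month ASES is not lower than the benchmark by more than θ. In the Path rows, write A − B ≥ −θ.
2. In the decision tables of Protocol 11.3.2 and SAP 3.1.1, replace the conclusions. For p ≤ 0.05: the central tendency (mean for the t-test, median for the sign test) is not lower than the benchmark by more than 20.33 (Arm A) / 11.08 (Arm B) points. For p > 0.05: non-inferiority not shown. Remove the H1 tag from the rejection row.

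**Should be changed with it**

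3. Report the difference from 58.74 / 74.48 with its 95% CI, and state that the benchmark is treated as fixed. In the sign-test branch use the CI of the median, and note that the benchmark is an average of means.
4. Write −θ = −20.33 / −11.08 throughout, with 38.41 / 63.40 as the test and null values. Reconcile the sidedness, and correct RSA to TSA/HA at 38.41.
5. State that the one-SD margin was set statistically, unless a clinical reason can be given.

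**Cost.** Items 1, 2, 4 and 5 are wording. Item 3 is a subtraction from the CI of the mean already planned, plus one extra output if the sign test is used. Tested values, enrolment and data collection stay as they are. The price is a more modest permitted claim.

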## 11. Statistical Methods

By clinical investigation arm, the 24 months postoperative results for subjects implanted with the ReUnion RFX System will be compared to a historical group and results reported by respective clinical outcome data in the scientific literature. The benchmark sources and values will serve as the control group for the ReUnion RFX System subjects. Hypotheses are developed for each of the two clinical investigation arms.

The Statistical Analysis Plan (SAP) lists all variables/questions within this clinical investigation. Therefore, no additional “evaluation” chapter is required nor needed for this CIP.

Data will be captured via IBM Clinical Development electronic data capture (EDC) system and statistical analysis will be performed using IBM SPSS. All statistical hypotheses tests will be with confidence levels ( $1-\alpha$ ) of 95% and power ( $1-\beta$ ) of 80%. The significance level ( $\alpha$ ) is 0.05 and the beta-value ( $\beta$ ) is set to 0.20. Therefore, p-values  $\leq 0.05$  will indicate statistical significance.

Results will be presented using summary tables and optionally supported by graphs. For detailed information per variable, see SAP.

The primary endpoint of the clinical investigation is to demonstrate non-inferiority of the device to the selected literature controls (benchmark), as measured by the ASES Shoulder Score at 24 Months post-operative.

[figure not shown]

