Acceptance Criteria for Sample Size Calculation		
Significance Level (<math>\alpha</math>)	0.05 (5%)	
Power (1-<math>\beta</math>)	0.80 (80%)	
Confidence Interval (CI)	0.95 (95%)	
Tails	2	
Path	Non-inferiority – ReUnion RFX Arm B (RSA) (A) $\geq$ Benchmark (B, explorative analysis in this document)	
Hypotheses Pair	Null ( $H_0$ )	$A - B < -\theta$
	Alternative ( $H_1$ )	$A - B \geq -\theta$
Benchmark Timepoint	24 months postoperative	
Benchmark no. of sources	5	
Benchmark Mean	74.48 (pooled mean ASES [points])	
Benchmark Std. Dev.	11.08 (pooled std. dev. ASES [points])	
Benchmark Value Non-Inferiority Margin (-<math>\theta</math>)	Pooled mean ASES minus pooled std. dev. ASES $74.48 - 11.08 = 63.40$ points	
Software Used	IBM SPSS Sample Power V3.0	
IBM SPSS Sample Power Output		
One goal of the proposed clinical investigation is to test the null hypothesis that the population mean is 74.48 points. The criterion for significance (alpha) has been set at 0.05. The test is 2-tailed, which means that effects in both directions will be interpreted. With the proposed sample size of 10 cases, the clinical investigation will have power of 80.3% to yield a statistically significant result. This computation assumes		

that the population from which the sample will be drawn has a mean of 74.48 points with a standard deviation of 11.08 points. The observed value will be tested against a theoretical value (constant, non-inferiority margin) of 63.40 points.

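### The 5% level of the primary test covers only a comparison with the fixed values 38.41 and 63.40, not the stated A - B hypothesis, because the benchmark's own standard error (3.97 in Arm A, 3.14 in Arm B) is left out

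*Protocol*

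**What the plan says.** Protocol section 11 says "The benchmark sources and values will serve as the control group for the ReUnion RFX System subjects". Section 11.3.2 sets the null hypothesis as A - B below the margin, describes it as a "comparison of the 24 months postoperative ASES Shoulder Score effectiveness/performance between the two underlying populations", and calls 58.74 and 74.48 estimates for the control group. The decision tables in that section phrase a significant result as the device being at least equal to the benchmark control. On the level it says "Hypothesis tests will be one-sided with a significance level" of 5%.

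The descriptives in 11.1.1 and 11.1.2 give each benchmark mean a standard error and a 95% confidence interval: 3.97185 and 47.71 to 69.77 in Arm A, 3.14124 and 65.76 to 83.20 in Arm B.

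The test itself is a one-sample t-test or a sign test, chosen by the normality assessment, against 38.41 (A) or 63.40 (B). The sample-size text for Arm A says "The observed value will be tested against a theoretical value (constant, non-inferiority margin) of 38.41 points", and Arm B has the same sentence with 63.40. SAP 3.1.1, 3.2 and 6.6 repeat this. Neither document carries the benchmark standard error into the test or plans a sensitivity analysis for it.

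**The concern.** The hypothesis contains two unknown means, but the test allows for sampling error in only one of them. The omitted part is not small. With 22 evaluable subjects the trial mean would have a standard error of about 4.33 in Arm A and 2.36 in Arm B, against 3.97 and 3.14 for the benchmark. If the true benchmark lies above the five-study average, the pass mark is too low for the A - B question, and an inferior result can be declared non-inferior more often than the stated 5%. A larger trial does not cure this: the trial's standard error shrinks and the benchmark's does not.

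**Working it through.** **Inputs.** Protocol 11.1.1: the Arm A population "has a mean of 58.74 points with a standard deviation of 20.33 points", benchmark SE 3.97185. Protocol 11.1.2: the Arm B population "has a mean of 74.48 points with a standard deviation of 11.08 points", benchmark SE 3.14124. Margins on the A - B scale: 58.74 - 38.41 = 20.33 and 74.48 - 63.40 = 11.08. Level: one-sided 5% (11.3.2).

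**Reproducing the plan's figures.** The five study means give 58.74 with SE 3.97185 (A) and 74.48 with SE 3.14124 (B), as printed. The plan states: "With the proposed sample size of 10 cases, the clinical investigation will have power of 80.3% to yield a statistically significant result". The effect size is 20.33/20.33 = 11.08/11.08 = 1.0. The noncentral t at n = 10 gives 80.31% two-sided, which matches, and 89.8% one-sided. The stated power therefore treats the benchmark as exact and uses a two-sided test.

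**Sample sizes examined.** 10 is the plan's calculated n. 22 and 50 are assumptions: 100 subjects split equally, less the 56% drop-out (50 × 0.44 = 22) or with no loss (50).

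**Error at the boundary, normal approximation.** With true A - B at the margin and trial SD equal to benchmark SD:

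error = P(Z > 1.645 × SE_trial / sqrt(SE_trial² + SE_benchmark²)), where SE_trial = SD/sqrt(n).

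Arm A, n = 22: SE_trial = 20.33/sqrt(22) = 4.334; sqrt(4.334² + 3.972²) = 5.879; 1.645 × 4.334/5.879 = 1.213; error 11.3%.

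Arm B, n = 22: SE_trial = 11.08/sqrt(22) = 2.362; sqrt(2.362² + 3.141²) = 3.930; 1.645 × 2.362/3.930 = 0.989; error 16.1%.

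**Exact t-test and sign test.** The t-test column integrates the noncentral-t rejection probability over a normal benchmark error, and simulation agrees. The sign-test column is simulated with normal data.

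| Arm | n | Normal approx. | t-test | Sign test |
|---|---|---|---|---|
| A | 10 | 8.1% | 7.7% | 1.9% |
| A | 22 | 11.3% | 10.9% | 5.8% |
| A | 50 | 16.7% | 16.5% | 10.6% |
| B | 10 | 11.0% | 10.3% | 2.9% |
| B | 22 | 16.1% | 15.6% | 9.0% |
| B | 50 | 23.1% | 22.9% | 16.3% |

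Against 38.41 or 63.40 taken as exact, the t-test error is 5%.

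**If the test were run two-sided at 5%.** The upper-tail t-test error becomes 4.3% (A) and 6.3% (B) at n = 10, 7.0% and 11.3% at 22, and 12.2% and 18.7% at 50, against a nominal 2.5%.

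**Including the benchmark SE.** With sqrt(s²/n + SE_benchmark²) and Satterthwaite degrees of freedom (4 for the benchmark), the error is 2.7% to 4.7% over these cases. Power at true equality is 82%, 96% and 99% in Arm A and 71%, 84% and 89% in Arm B at n = 10, 22 and 50. With 1.645 as the critical value instead, the error is 5.0% to 6.0%.

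**On the score scale, n = 22, s equal to the benchmark SD.** The planned t-test passes at an observed mean of 38.41 + 1.721 × 4.334 = 45.87 (A) and 63.40 + 1.721 × 2.362 = 67.46 (B). With the benchmark SE included (about 15.1 and 9.2 degrees of freedom) the pass marks are 38.41 + 1.752 × 5.879 = 48.71 and 63.40 + 1.828 × 3.930 = 70.58.

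**The case against.** The strongest reply is that the pass marks were fixed in advance and the sample-size text itself calls them constants. A goal derived from literature is still a prespecified goal, and against it the t-test holds its 5%. That stands. It does not remove the mismatch, because 11.3.2 and SAP 3.1.1 state the hypothesis and the conclusion against the benchmark population, not against a goal. The wording or the analysis has to change.

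A reader might infer that the true error rate is simply 11-23%. The documents do not support that. The range needs 22 to 50 evaluable subjects per arm, while the plan gives only a total of 100, and at its own n of 10 the t-test figures are 7.7% and 10.3%. It also needs the t-test branch: under the sign test at n = 10 there is no inflation above 5%. And it needs the one-sided reading of 11.3.2, whereas the sample-size section says "The test is 2-tailed, which means that effects in both directions will be interpreted".

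It is also fair that the harm runs both ways. If the true benchmark is below the five-study average, the pass mark is too strict. The error rates above average over both directions. Finally, the benchmark SE rests on five unweighted means and is itself imprecise.

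That the margin absorbs the benchmark's uncertainty is not a good answer. The margin is the average within-study SD and sets the boundary. The error rate is evaluated at that boundary.

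**Conclusion.** The concern holds in a limited form. The stated 5% is correct for a t-test against 38.41 or 63.40 as fixed numbers. It does not carry over to the A - B hypothesis as written. For that hypothesis the one-sided t-test error is about 8% (A) and 10% (B) at n = 10, and about 11-16% (A) and 16-23% (B) at an assumed 22 to 50 evaluable per arm. The sign test gives about 2-3%, 6-9% and 11-16% at 10, 22 and 50. All these figures take the trial SD equal to the benchmark SD and use the plan's benchmark SE as given. The finding does not show that the planned test is invalid for a fixed goal.

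**What to change.** In Protocol 11.3.2 and SAP 3.1.1 and 6.6, choose one of two routes.

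1. Declare 38.41 and 63.40 fixed performance goals, remove the two-population wording and the conclusion phrased against the control, and say that the 5% level applies only to those goals. This costs a text edit and narrows the claim.
2. Keep the A - B hypothesis. Beside the planned test, report a one-sided 95% lower bound for A - B with SE = sqrt(s²/n + SE_benchmark²), using 3.97 (A) and 3.14 (B) and Satterthwaite degrees of freedom with 4 for the benchmark, compared with -20.33 and -11.08. State that the 5% level of the fixed-value test takes the benchmark as exact.

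Route 2 is one line of calculation per arm from figures already in the plan. Its price is a less favourable bound and some power: about 96% (A) and 84% (B) at 22 evaluable under true equality. The bound concerns means, so if the sign test is selected it is a supplementary result and not a correction of that test. It also takes the margins as exact, although they come from the same five studies.
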